Document date 20161017

Statistical analysis plan for

Increased Adherence to Physical Activity on Prescription (FAR) through mindfulness - a randomized study in primary care (FAR-MIND)

Statistical Analysis Plan (SAP)

Power calculation

A sample size of a full-scale intervention study with a follow-up time of 12 months was calculated on a 1:1 relationship between two groups (PAP and combination) and estimated to n = 375 in each group, based on a power analysis with 5% significant-level and a power of 80%. Dropout was expected to be 30%. The calculation was based on other studies with self-reported compliance to PAP as an outcome measure, where 50% of the participants followed the recommendation on physical activity from the PAP. We estimated an increase from 50% to 62.5% of self-reported adherence to PAP. The pilot-study sample size is based on the assumed patient flow and due to a limited project budget. In this pilot study, we aimed to include approximately 30 participants in each arm, which is in concordance with a general flat rule, using a minimum of 30 participants to be able to estimate a parameter.

Randomisation

The randomisation of the three intervention groups (PAP, combination, mindfulness) was stratified by the patients' age and sex, with three age groups: 40–49, 50–59 and 60–65 years. The randomisation was done by a minimisation method with a random element; as minimisation variables in the randomisation, we used age and sex to get the groups as equal as possible. The randomisation was done in the statistical programme STATA version 15 (StataCorp, College Station, TX).

intervention outcome

All measurements and questionnaires were collected at baseline, after 3 months and after 6 months.

The primary intervention outcome was a change in the level of physical activity, self-reported and measured by ACTi Graph GT1X activity monitors. We used the same definitions and methods to handle the activity monitor data as in previously published research regarding physical activity [1, 2]. Activity monitor data were divided into sedentary, light physical activity (LIPA) and moderate to vigorous physical activity (MVPA). The participants were instructed to wear the activity monitor daily for a week before randomisation, at 3 months and at 6 months follow-up. Wear time was defined by subtracting non-wear time from 24 hours. Non-wear time was defined as at least 60 consecutive minutes with no movement (0 counts per minute), with allowance for a maximum of 2 min of counts between 0 and 100 [1, 3]. We considered ≥ 600 min wear time per day for at least 4 days to be valid compliance [1, 2]. Due to a small sample size, we did not demand four consecutive days with valid wear time, and we did not differ between weekdays and weekends. The average was expressed as total counts divided by wear time in minutes per day (counts per minute) and averaged over worn days. Registrations below 100 counts per minute were determined as being sedentary [1, 2, 4]. 100-2019 counts per minute were considered LIPA, and > 2020 counts per minute as MVPA [1, 2]. The results are presented as percentage sedentary, LIPA or MVPA per valid day and averaged over the number of valid days [2] self-reported daily activity (e.g. gardening, slow walks, biking) was measured by an eight-step scale ($0 = 0 \text{ min/week}, 7 \ge 300 \text{ min/week}$), and selfreported leisure time activity (e.g. running, football) was measured by a seven-step scale (0 =0 min/week, $6 \ge 200$ min/week).

Secondary intervention outcomes

Change in self-rated health (SRH) between baseline and follow-up, measured with a five-step scale (1–5): very poor, poor, fair, good or very good.

Change in blood pressure, weight or serum lipids between baseline and follow-up.

Change in insomnia problems as measured with insomnia severity index (ISI) [5] between baseline and follow-up.

Change in mindfulness was measured with five facets of the mindfulness questionnaire (FFMQ) [6] between baseline and follow-up.

Statistical methods

Group comparison analysis will be conducted using the chi-square test for categorical variables. Quantitative variables will be analyzed using ANOVA or Kruskal-Wallis for normally distributed and non-normally distributed variables, respectively. Relationships between different variables will be examined using regression analyses

The intervention effect on changes in outcome measures will be examined by analysing average group differences (PAP, combination, mindfulness) in baseline score and change in each outcome between baseline and 3- and 6-month follow-up using a linear mixed-effects model. Each model included the time variable and group as indicator variables and an interaction between time and group to estimate treatment differences in change over time, adjusted for baseline measures and considering the correlation between repeated measurements. We will not adjust for the minimisation variables from the randomization in the analysis. Statistical analyses were done using STATA version 15 (StataCorp, College Station, TX).

 [PMC free article] [PubMed] [Google Scholar]

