The guidelines cover both primary prevention, i.e. health counselling for healthy and at-risk groups, and secondary prevention for those already diagnosed with a disease. The mission of primary care, which is to prevent illness and worsening of pre-existing disease, is important for each individual, but also from a socio-economic perspective. Secondary preventive work has been actively conducted for many years in primary care with diabetes clinics, hypertension clinics, asthma/COPD clinics and clinics for smoking cessation.

Despite the fact that there is a clear disease prevention mission and knowledge that physical activity counteracts the onset of so-called well-being diseases, the inactive time is generally increasing in the population.

Purpose

To investigate whether mindfulness can increase adherence to FAR® in inactive individuals.

More specifically, we intend to:

1. Study whether mindfulness can strengthen adherence to FAR®, i.e. increase the amount of physical activity and reduce physical inactivity.

2. Study the effect of intervention on measured vital signs, routine blood tests, self-rated health, sleep and lifestyle habits.

3. Study the effect of intervention on biomarkers e.g. inflammation markers (cytokines), microRNA and telomeres as well as the relationship between biomarkers and physical activity/inactivity.

Hypothesis

- The main hypothesis is that Mindfulness increases the compliance of inactive individuals and leads to a increased physical activity and reduced inactivity.
- Hypothesis 1: Self-perceived sleep problems decrease and self-perceived health increases after mindfulness/FAR®-intervention.
- Hypothesis 2 The intervention with FAR/® mindfulness affects biomarkers (e.g. cytokines, miRNAs, telomeres) in individuals with low levels of physical activity.

Studies

The following describes the implementation of the research project in the health choice units involved. The project, which consists of an intervention, will run from September 2016 until December 2018 at the latest. The project starts with a pilot study that ends after 6 months of follow-up. The health choice units involved will ask all individuals seeking care and are between 40-65 years old if they want to participate in the study

Inclusion/exclusion

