[figure not shown]
Samples for freezing

Participating health choice units perform venous sampling of the research samples according to the sampling kits sent out. This also means assisting in sending the marked test tubes to the laboratory for further handling and transport to the CPF. This refers to sampling before and after intervention and during follow-up. This means sampling at 0 months, 3 months, 6 months and at full study also at 12 months, which means four occasions per participant.

Tests and procedures

In vitro kits, including referrals, instructions and labels for labelling, will be prepared at the CPF laboratory and packed in boxes, one per participant and sampling. These boxes will be distributed to the participating health choice units. The unused tubes should be returned to the CPF after the study is completed. A detailed annex to instructions will be prepared by the CPF. The samples to be submitted to the CPF are marked with the date and the participant's serial number. Blood volume is 36 ml per test batch, a total of 108 ml after three rounds of tests and 144 ml after four rounds. It must be noted in the patient's medical record that samples have been taken as part of a research study.

Study Flowchart

Outcome measures

Association between self-rated health, lifestyle habits, heredity for cardiovascular disease, physical activity level, vital parameters and blood tests.

Change in physical inactivity and activity

Difference in inactivity between intervention group and control group as measured by accelerometer

Change in self-rated worry and anxiety according to PHQ 9 after intervention

Change in Conscious Presence According to FFMQ After Intervention

Change in sleep according to ISI after intervention

Differences in biomarker levels between the different intervention groups

Power calculation

We will carry out a pilot study in order to make a more accurate power calculation which will be based on the results of the pilot study (89). We plan to include 30 people per group in the pilot study, a total of 90 people.

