The sample size for a full-scale intervention study with follow-up is based on a 1:1 ratio between the groups and calculated to N=321 in the intervention group and N=321 in the control group per group based on a power analysis with 5% significance level and 80% power. The non-response rate is calculated at about 30%. The calculation is based on other studies with compliance to physical activity on prescription as an outcome measure, where 50% of the individuals followed the recommendation on physical activity based on FAR,@ we expect an increase of 25% from 50% to 62.5% adherence

Data analysis

Group comparison analysis will be conducted using chi-2 test for categorical variables. Quantitative variables will be analyzed with ANOVA or Kruskal-Wallis prenormal-distributed and non-normally distributed variables, respectively. Correlations between different variables will be investigated using regression analyses (90).

Safety and ethical aspects

Participants in all groups are contacted by a doctor according to a flow chart if abnormal measurements appear or if physical symptoms occur during intervention that need to be assessed by a doctor. Conversations about lifestyle habits can raise thoughts and concerns about personal health, and if necessary, there will therefore be the opportunity to get feedback via the district nurse or your regular doctor. Personal identity number and name will be replaced with a serial number that follows the form and

samples through the study, which means that all data during analysis is completely without personal data and only marked with serial number. The identification lists will be kept at the health choice units until the analyses are completed, after which the identification lists will be stored at the CPF in a secure manner so that no unauthorised person can access them. Presentation of results from the study will take place at group level, which means that it is not possible to identify individuals. The individuals included in the study are covered by the Patient Injury Act (1996:799) as they are patients at visits to the health choice unit and are covered in clinical research by the same protection as if they were only patients. The study has received ethical approval from the Regional Ethics Review Board in Lund (2016/404). The study is registered on clinicaltrials.gov(20160826) rainr NCT02869854.

Economics

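### The full study's 80% power is for an adherence rate that neither outcome list contains or defines, the Protocol's N falls short of it, and the pilot's effect is not barred from resetting the target

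*SAP*

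**What the plan says.** **Size and power.** The SAP (Power calculation) gives a full study with 12 months of follow-up, "calculated on a 1:1 relationship between two groups (PAP and combination) and estimated to n = 375 in each group", at 5% significance, 80% power and 30% dropout. It names the endpoint openly: "The calculation was based on other studies with self-reported compliance to PAP as an outcome measure". The assumed rates are 50% and 62.5%. The Protocol (Power calculation) uses the same rates, "we expect an increase of 25% from 50% to 62.5% adherence", with the same significance level and power and about 30% non-response, but gives 321 per group.

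**What adherence means.** The Protocol's Purpose section glosses adherence as to "increase the amount of physical activity and reduce physical inactivity". Its Power calculation takes the 50% from studies "where 50% of the individuals followed the recommendation on physical activity". Neither passage gives a cut-off, a question or a time point.

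**Listed outcomes.** The Protocol's Outcome measures include "Change in physical inactivity and activity" and "Difference in inactivity between intervention group and control group as measured by accelerometer", but no adherence rate. The SAP (intervention outcome) states: "The primary intervention outcome was a change in the level of physical activity, self-reported and measured by ACTi Graph GT1X activity monitors". It then describes sedentary, light and moderate-to-vigorous percentages and two stepped self-report scales. Its secondary outcomes contain no adherence rate either.

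**Role of the pilot.** The Protocol's Introduction makes the size of the effects to be expected one of the pilot's aims. Its Power calculation and Timetable sections say that the full study will be sized from pilot results. The SAP puts the pilot at about 30 per arm.

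**The concern.** A power figure is a statement about one endpoint, one contrast and one target difference. Here the 80% belongs to a proportion that the plan does not list and cannot score, while the outcome that is listed has no target difference or SD. As written, the 80% cannot be claimed for any listed outcome. A null result on activity could not be read against it, and a positive adherence result would depend on a definition chosen later.

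The second part concerns the update after the pilot. If the observed pilot effect may serve as the new target, a chance high value makes the full study too small and a chance low value makes it needlessly large or leads to its being dropped. The Protocol does not say which parameters the update may change.

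**Working it through.** **Inputs.** From both Power calculation sections: rates 0.50 and 0.625, significance 5%, power 80%, loss 30%. Sidedness is not stated. Two-sided is assumed, because one-sided variants give 278 or 300 per group after loss, not 375.

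**1. Reproducing the stated sizes.** With pooled rate 0.5625:

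n = [1.960 × √(2 × 0.5625 × 0.4375) + 0.842 × √(0.2500 + 0.2344)]² / 0.125² = [1.960 × 0.7016 + 0.842 × 0.6960]² / 0.015625 = 246.1, so 247 per group.

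With continuity correction: (246.1/4) × [1 + √(1 + 4/(246.1 × 0.125))]² = 261.8, so 262.

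- SAP: 262 / 0.70 = 374.3, so 375. Reproduced.
- Protocol: 247 × 1.3 = 321.1, so 321. Reproduced, without the correction and with loss multiplied up instead of divided out.

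Both sizes therefore match this binary comparison.

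**2. Power left after 30% loss, for the adherence rate.** Power = Φ{[0.125 × √n − 1.960 × 0.7016] / 0.6960}; with continuity correction, 0.125 becomes 0.125 − 1/n.

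| Stated N | Evaluable | Power, uncorrected | Power, corrected |
|---|---|---|---|
| 375 (SAP) | 375 × 0.70 = 262.5 | 82% | 80% |
| 321 (Protocol) | 321 × 0.70 = 224.7 | 76% | 73% |

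**3. What those numbers mean for a continuous activity measure (illustration only).** No SD or target is given, so only a standardised difference can be shown, in units of the SD at follow-up. Detectable with 80% power, unadjusted: (1.960 + 0.842) × √(2/n) = 0.264 at 225 and 0.245 at 262.

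The SAP's mixed model adjusts for baseline. As an approximation, multiply by √(1 − r²), where r is the baseline-to-follow-up correlation. The documents give no r; 0.5 to 0.7 is an assumption.

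- r = 0.5 (factor 0.866): 0.229 at 225, 0.212 at 262.
- r = 0.7 (factor 0.714): 0.189 at 225, 0.175 at 262.

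The range is thus about 0.25–0.26 SD unadjusted and 0.18–0.23 SD adjusted. Whether such differences are plausible or worthwhile cannot be judged from the documents.

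**4. Precision of the pilot effect.** The 95% half-width at 30 per arm is 1.96 × √(2/30) = 0.506 SD unadjusted, 0.506 × 0.866 = 0.44 at r = 0.5, and 0.506 × 0.714 = 0.36 at r = 0.7. Against the detectable differences in step 3, that is 0.506/0.264 = 1.9 to 0.506/0.245 = 2.1 times as large. The ratio is the same with adjustment, since both terms shrink by the same factor. All 30 are taken as evaluable; any loss widens the interval.

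**The case against.** **The SAP hides nothing.** It names self-reported adherence in the same paragraph as the 80%. A reader might infer that the 80% is presented as covering the activity outcome; the text does not support that. What stands is narrower: the named rate is not listed or made operational.

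**Adherence is not wholly undefined.** The Purpose section ties it to activity, activity is measured, and the Protocol's Inclusion/exclusion section states limits of 150 and 75 minutes per week. A rate could be built from these, and the SAP's chi-square test could analyse it. But the plan does not link them, and the chi-square provision is generic.

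**The full study is provisional.** This is the strongest objection. The Protocol promises a better calculation after the pilot, and the SAP's 3- and 6-month model describes the pilot. A reader might infer that the missing 12-month analysis is a defect; it is staging. The model can also estimate PAP vs combination, although it does not name that contrast as primary. Even so, the sizes and the 80% are stated now, and limits on the use of pilot results are best set before those results are seen.

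**Nothing says that the observed effect will become the target.** Correct. A reader might infer that the sponsor intends this; the documents only leave it open.

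**Unadjusted figures overstate the problem.** This also stands, so baseline-adjusted ranges are shown beside them.

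**Conclusion.** The point holds, with moderate weight. The 80% applies to a 50% vs 62.5% adherence proportion that is in neither outcome list and has no scoring rule. It is not established for change in physical activity. It is delivered by the SAP's 375 (80% corrected, 82% uncorrected after 30% loss) but not by the Protocol's 321 (about 76% uncorrected), so the Protocol's N falls short even for adherence.

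It would go too far to say that the full study is underpowered for activity. Without an SD and a target difference, that cannot be shown either way. The 0.25–0.26 SD and 0.18–0.23 SD figures are illustrations that rest on equal SDs, a simple two-group comparison and, for the second range, an assumed correlation.

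On the pilot, a half-width of about 0.5 SD (0.36–0.44 SD with the assumed adjustment) is too wide to set a target difference in either direction. The gap is the absence of a limit on what may be updated, not a stated plan to misuse the estimate.

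**What to change.** 1. **One primary for the full study, in the full-study plan.** Choose one of two.
   - An adherence rate at 12 months, combination vs PAP, with a definition that matches the studies behind the 50% and 62.5%. One example is meeting the 150 or 75 minutes per week limits on the SAP's self-report scales, after checking that those limits fall on step boundaries; the SAP shows only the end points of the scales.
   - One activity measure, with its target difference and SD, and a sample size computed for it.
2. **Until then**, state in both documents that the 80% applies to the adherence rate and not to the activity outcome. Reconcile 321 with 375, with the loss adjustment shown.
3. **Limit the pilot update.** State that the pilot informs retention, monitor wear compliance, SDs and, roughly, the control rate. State that its observed effect will not replace the full study's target difference.

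**Cost.** Mainly wording. The price is that one measure carries the confirmatory claim and that the 80% can no longer be quoted for the activity outcome. Using 375 in place of 321 would add 54 participants per group (375 − 321).

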Individuals between the ages of 40-65, regardless of why they visit any of the committed health choice units, will be asked to participate by asking if they are insufficiently physically active (<150 minutes per week at moderate intensity or <75 minutes per week at high intensity).

Exclusion Criteria: Dementia, severe mental disorder, new-onset untreated untreated unstable anginapectoris, or myocardial infarction within 6 weeks prior to study entry. Those with physical disabilities that prevent physical activity and individuals who do not master the Swedish language in speech and writing will be excluded. Patients who have abnormal values according to guidelines that require same-day or weekly medical consultation.

Procedure Inclusion

At the care units, everyone who visits will be asked about study participation. There will be posters with information at the entrances and in other suitable places. Those who wish to participate in the study agree to this by signing informed consent after receiving oral and written information. Information about the study will be provided by the district nurse/nurse involved in the study, who will then also collect the informed consent. The opportunity to ask questions about the study will be repeated at subsequent visits as well as an opportunity to discontinue their participation. The potential research subject should estimate their physical activity level in minutes per week for inclusion assessment. The research subjects are asked to come one morning for fasting blood sampling.

Measurement methods

Physical activity; Health-promoting physical activity is any physical activity that improves health and physical capacity without causing harm or posing a risk. The international recommendation of the WHO (2011) (38) is at least 150 minutes of physical activity per week at moderate intensity, or at least 75 minutes at high intensity. Intensity refers to how strenuous the activity is. Moderate intensity refers to housework, gardening, brisk walks or the like. High intensity refers to running, swimming, aerobics, or similar.

Accelerometer: The Actigraph GT3X is a digital motion meter that will be attached to the subject at waist height. The accelerometer records the time in motion as well as the time inactivity. Over a seven-day period, about 40,000 measurement points are collected per accelerometer.

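### The mixed model leaves out the minimisation factors without a reason and does not settle how baseline enters, so intervals may be wider than necessary

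*SAP*

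**What the plan says.** SAP, Randomisation: the three arms were allocated by minimisation with a random element, "as minimisation variables in the randomisation, we used age and sex to get the groups as equal as possible". The age bands are 40–49, 50–59 and 60–65 years.

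SAP, Statistical methods: "We will not adjust for the minimisation variables from the randomization in the analysis". No reason follows, and the protocol gives none.

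The same SAP section describes the mixed model in three ways:

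- It works by "analysing average group differences (PAP, combination, mindfulness) in baseline score and change in each outcome between baseline and 3- and 6-month follow-up".
- It contains "an interaction between time and group to estimate treatment differences in change over time, adjusted for baseline measures".
- It has indicators for time and group and allows for correlation between repeated measurements.

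It does not say whether the baseline visit is a level of the time variable, whether baseline is a covariate, or whether arm means are constrained equal at baseline. The protocol's Data analysis section lists only chi-square tests, ANOVA or Kruskal-Wallis, and regression, so it does not settle the matter.

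This is the stated analysis of the main endpoint: "The primary intervention outcome was a change in the level of physical activity" (SAP, intervention outcome).

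**The concern.** There are two separate points.

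**Omitted factors.** Minimisation balances age and sex across arms and so removes their contribution to the true variability of the arm difference. A model without them leaves that contribution in the residual. To the extent that age and sex predict the analysed quantity, the reported standard error exceeds the true one.

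**Baseline.** The wording permits two models, and they differ.

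- *Baseline as a response row.* Time × group is then the difference in change from baseline. With complete data it equals the raw change-score contrast, and adding baseline as a covariate does nothing to it. The stated adjustment brings no precision.
- *Only 3- and 6-month rows as responses, with baseline as covariate.* The precision gain is kept, but time × group is now the 6-month effect minus the 3-month effect. The treatment effect is the group contrast at each visit. An analyst who followed the SAP literally and read the effect from the interaction would report a different quantity.

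At stake is interval width in a pilot of about 30 per arm, and an estimator that could be chosen after the data are seen. The protocol also wants "a more accurate power calculation which will be based on the results of the pilot study".

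**Working it through.** **The plan's own figure.** The only planning number in the SAP is the full-scale size. For 50% against 62.5%, two-sided 5% and 80% power, the continuity-corrected formula gives 262 per group, and 262/0.70 = 374.3, rounded up to 375. This matches the SAP. It concerns a binary two-group comparison and says nothing about the mixed model's precision. The documents give no SD, correlation or interval width for that model.

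**Inputs from the documents:** three arms, about 30 each (SAP, Power calculation), 88 included (Protocol, Timetable), minimisation on sex and three age bands, visits at 0, 3 and 6 months.

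**Assumed inputs:** minimisation probability 0.8; baseline-to-follow-up correlation ρ; ratio r of baseline SD to follow-up SD; share R² of follow-up variance given baseline that age and sex explain.

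**1. Leaving out age and sex.** Simulated minimisation, N = 90, 6,000 runs per setting (Monte Carlo error about 0.3 points), baseline as covariate, factors omitted:

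| R² (assumed) | Size of 5% test, ρ = 0.5 | Size, ρ = 0.7 | Model SE above true SE |
|---|---|---|---|
| 2% | 4.8% | 4.7% | under 1% |
| 5% | 4.5% | 4.7% | 1–2% |
| 10% | 4.0% | 4.6% | 3–5% |
| 20% | 3.1% | 3.3% | 10% |

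With the factors included, size is 4.8–5.8%. At R² = 20% and ρ = 0.5 the model SE is 0.225 against a true 0.204 without the factors (0.225/0.204 = 1.10), and 0.201 against 0.202 with them. If the age and sex effects are stable over time, little is lost: size is 4.7–5.2% for change scores and 4.3–4.8% with a baseline covariate.

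A second simulation (88 patients, 3,000 runs, ρ = 0.5) compared interval widths, unadjusted over adjusted, at R² = 0, 5, 10 and 20%:

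- no dropout: 0.998, 1.024, 1.052, 1.117
- 30% dropout: 0.988, 1.014, 1.043, 1.108

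These follow the approximation 1/√(1−R²), which gives 1.000, 1.026, 1.054 and 1.118. When age and sex explain nothing, adjusting for them costs about 1% or less.

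**2. The role of baseline.** The variance of a change-score contrast relative to a baseline-adjusted contrast is (1 + r² − 2ρr)/(1 − ρ²). Interval width scales with its square root.

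| r | ρ | Variance ratio | Change-score interval wider by |
|---|---|---|---|
| 1 | 0.5 | 1.00/0.75 = 1.33 | 15% |
| 1 | 0.7 | 0.60/0.51 = 1.18 | 8% |
| 0.8 | 0.5 | 0.84/0.75 = 1.12 | 6% |
| 0.8 | 0.7 | 0.52/0.51 = 1.02 | 1% |

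The r = 0.8 rows matter because patients "will be asked to participate by asking if they are insufficiently physically active" (Protocol, Inclusion/exclusion), which may narrow the spread at baseline.

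SE of the contrast under each reading, by generalised least squares (30 per arm, ρ = 0.6, unit SDs, complete data):

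| Model | SE |
|---|---|
| Baseline as a response row, arm means free | 0.2309 |
| The same plus a baseline covariate | 0.2309 |
| The same plus age and sex main effects | 0.2309 |
| Baseline as a response, arm means constrained equal | 0.2066 |
| Follow-up rows only, baseline × time as covariate | 0.2080 |

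By hand, √(2 × 0.4 × 2/30) = 0.2309 and √(0.64 × 2/30) = 0.2066. The 0.2080 differs from 0.2066 only through chance baseline imbalance in the simulated covariate.

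**The case against.** The omission of age and sex is prespecified and disclosed, and at shares of 2–5% the loss lies within about two Monte Carlo errors of nothing. Nothing in the documents suggests that age band and sex explain 10% or 20% of follow-up activity given baseline among inactive people aged 40–65. This stands: the clear loss appears only at an assumed 20%.

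The model can also be read coherently. Group is the baseline difference, time × group is the difference in change, change is the stated outcome, and the mention of baseline adjustment is loose wording. That model is valid and unbiased, so preferring a baseline-adjusted one is a choice of efficiency. This also stands, but the adjustment clause then has no function and another analyst could reasonably fit a different model.

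Three further limits hold. The losses in parts 1 and 2 must not be added, because the first was simulated with baseline as covariate and the second arises under the other reading. The 15% and 8% figures need equal SDs. The link to full-scale planning is loose, since the power calculations shown use binary adherence and do not take the mixed-model interval width as an input.

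None of this supplies a reason for omitting the factors or settles which model is meant.

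**Conclusion.** The concern holds on both counts: allocation factors are left out of the analysis without a reason, and the text does not define one model. The consequence is conservative only, with no bias and no inflated type I error.

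The size depends on quantities the documents do not give. Leaving out age and sex ranges from negligible (R² of 5% or less, or effects stable over time) to a standard error about 10% too large at R² = 20%. The change-score reading costs between 1% and 15% in interval width over ρ of 0.5 to 0.7 and baseline SD ratios of 0.8 to 1. The baseline ambiguity is the more consequential of the two, because it also decides which coefficient is the treatment effect. In a pilot with no power target of its own this is a precision and specification defect that should be corrected, not a threat to validity.

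**What to change.** Write out one model in SAP, Statistical methods. Either would do:

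1. **Follow-up values as responses.** Use the 3- and 6-month values as responses, with baseline × time as covariate and age band and sex as fixed effects. Take the effect from the group contrast at each visit.
2. **Baseline kept as a response.** Constrain arm means equal at baseline and add age band × time and sex × time terms. Main effects of age and sex alone leave time × group unchanged in the unconstrained model.

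The options differ when baseline is missing. The first drops anyone without a valid baseline accelerometer recording (at least 4 days of 600 minutes) unless it is imputed; the second keeps them.

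Report the combination-minus-PAP difference with its interval at each visit. If age and sex are to stay out, state why and add an adjusted sensitivity analysis.

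The cost is SAP wording and a few model terms, with no new data collection. Age band (2) and sex (1) add 3 parameters in the first option, besides the visit-specific baseline slope, and 3 × 3 visits = 9 in the second.
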